#### 8.3.4.2 Covariate

For any covariate, continuous or categorical, if values are missing for more than 15% of the subjects, the covariate will be omitted from the analysis.

As a general rule for missing baseline covariates, unless considered inappropriate, the population median baseline value for continuous covariates, or the most conservative category for categorical covariates will be imputed.

For time varying covariates, if any, data will be imputed within individual using the last observation carried forward (LOCF) method.

#### 8.3.4.3 Design variables

Observations (or subjects) with missing information on amount of drug administered, dosing date or time and sampling date or time will be excluded unless strong evidence can determine that drug was administered (e.g. confirmation by the Investigator that the drug was really administered either in a monitoring report or the data-review report). In that case theoretical date and time of dosing or sampling will be used.

	PH21036 / GDX-44-015 Analysis Plan Version 2.0: 29/10/2024	gadopiclenol Page 14/30
---	---	----------------------------

### 8.3.5 Data cleaning and detection of outliers

An outlier is an aberrant value that significantly deviates from the rest of the values.

Data review will be performed to identify potential errors in the data variables that will be used for the popPK analysis. Errors of this type would include, but not be limited to, missing data, inconsistencies between scheduled PK sampling times and actual sampling times, obvious suspected errors in recording of dates and/or times (resulting in negative estimates of actual times, for example), physiologically unreasonable covariate values, and unit of measurement errors.

Outlier sampling detection in PK profiles is mainly based on graphical representation as individual spaghetti plots by relevant groups. In sparsely sampled PK data, population and individual weighted residuals will also be considered in the identification of potential outliers.

A large deviation of a unique observation from adjacent observations within a PK profile, or an absolute value above 6 of weighted residuals justifies a point review. If inconsistencies are confirmed (i.e.: unphysiological value, etc.) the point, as an outlier, will be excluded of the analysis or included in a sensitivity analysis.

If the entire individual PK profile is unreliable to the expected PK behavior, and no other factors (co-administration of other drugs, noncompliance, extreme covariate values, etc.) could definitely explain the deviation, the entire data from the subject will be excluded, or included in a sensitivity analysis, to prevent potential bias into the analysis.

## 9 MODEL DEVELOPMENT

PopPK parameters will be estimated by non-linear mixed effect modelling using NONMEM. Mixed effects models describe the influence of both fixed effects and random effects. The random effects are typically used to capture the variability which can be split in residual variability (error) and between subject variability.

The population model will be defined by 4 basic components:

1. The structural popPK model components, which defines the PK parameters and describe the plasma concentration-time profiles of gadopiclenol.
2. The inter-individual error model component, which describes the inter-individual variation (IIV) in PK parameters after correction for fixed effects.
3. The residual error model component, which describes the underlying distribution of the error in the measured concentrations.
4. The covariate model component, which describes the influence of fixed effects (i.e., demographic factors) on PK parameters.

As a popPK model for gadopiclenol was already developed, this model will be used as starting point for the pediatric population (< 2 years old) with the objective to enrich and update the existing model if possible.

### 9.1 SEQUENCE OF PLANNED ANALYSIS

The popPK model will be developed according to the following strategy:

1. Preliminary checks will be performed to assess whether the existing model is predictive of data collected in pediatric patients <2 years. If it is the case, data from these pediatric patients will be

	PH21036 / GDX-44-015 Analysis Plan Version 2.0: 29/10/2024	gadopiclenol Page 15/30
---	---	----------------------------

added to previous data in order to update the existing model, otherwise, only pediatric population <2 years data will be used for model development

2. On the selected dataset (only pediatric population <2 years or pediatric population <2 years added to previous data), selection of the simplest structural model, which predicts the plasma concentrations as a function of time and dose, based on smallest objective function and by the pattern in the residual plots. The best estimation method, the most appropriate IIV models, and the residual error model, will be identified. The resulting model is called BASE. In this model, population specificities will be accounted for as structural covariates.
3. Graphical exploration of the covariates: between individual covariates and post-hoc (FO) or conditional (FOCE) parameter estimates and between covariates and conditional weighted residuals (CWRES).
4. Determination of the covariate model using a backward deletion process:
  - a. Univariate analysis (covariates are added only to parameters having  $\eta$  in BASE).
  - b. Multivariate analysis: all selected covariates are added together, the model is fit to data and a new value of objective function (OFV) will be obtained and considered as a reference called FULL model
  - c. Selection of significant covariate to obtain the FINAL model

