## 9.2 PRELIMINARY CHECKS

In order to check if the existing model is predictive of data collected in pediatric population <2 years, some preliminary checks will be performed.

First, gadopiclenol concentrations in pediatric patients <2 years will be simulated using the existing model (see model definition in Section 9.3) and actual patients' settings (dose, sampling, characteristics). A prediction-corrected performance visual checks (pcVPC) approach will be used, simulating 1000 replicates of pediatric patients <2 years and plotting the distribution of these simulated concentrations with the actual measured concentrations. The pcVPC approaches are defined in Section 10. The measured concentrations should be fairly distributed within the simulated distribution.

In a second step, the existing model will be applied to pediatric population <2 years data with model's parameters fixed to the final estimates obtained in previous data. The variability terms (IIV and residuals) will be estimated. Diagnostic plots (as defined in Section 9.8) will be used to assess model misspecification.

Should any interim evaluation need to be performed during the course of the study to determine if exposure in any group of pediatric patients <2 years is as expected, the first step based on pcVPC will also be used for this purpose.

[figure not shown]

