## 9.3 STRUCTURAL PHARMACOKINETIC MODEL

The population PK model selected on previous data was a two-compartment model with elimination from the central compartment. The model was parameterized in terms of clearance (CL), central volume of distribution ( $V_1$ ), inter-compartment clearance (Q) and peripheral volume of distribution ( $V_2$ ). All parameters were scaled to body weight using fixed allometric rules. The CL was also scaled to eGFR with a power model for pediatric population and a Gompertz function for adult population. Ethnic population covariate was

	PH21036 / GDX-44-015 Analysis Plan Version 2.0: 29/10/2024	gadopiclenol Page 16/30
---	---	----------------------------

applied on all parameters. Exponential models were used to describe the inter-individual variability on CL,  $V_1$  and  $V_2$  and a proportional model was considered as error.

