**Figure 1 Structural Gadopiclenol Population PK model**

Further to the submission of gadopiclenol application to health authorities, it was requested by EMA to replace the two equations used to estimate the influence of eGFR on CL of adults and children by a single equation based on serum creatinine (Screat) instead of eGFR. The model used for the application was the one model built on studies GDX-44-003, GDX-44-005 and GDX-44-007 (i.e. without study GDX-44-013 in Japanese volunteers).

Such model was obtained and the relationship between Screat and CL was best described with a 3 parameters Gompertz function as follows:

$$CL_i = \theta \times (1 - A \times \exp(-\exp(-B \times (Screat - C)))) \times \exp(\eta)$$

Where A=asymptote value, B=growth rate and C=inflexion point.

Parameters estimates are presented in Table 2.

	PH21036 / GDX-44-015 Analysis Plan Version 2.0: 29/10/2024	gadopiclenol Page 17/30
---	---	----------------------------

**Table 2 Gadopiclenol population PK model parameters estimates from the model refined for EMA submission and using Serum creatinine as covariate to describe renal function impact on CL**

Parameter	Estimate (%RSE)	95% CI	Variability (CV%) Correlation (R%)
$CL(L/h) = \theta_1(Weight/70)^{0.75} * (1 - \theta_5 * EXP(-EXP(-\theta_6 * (Screat - \theta_7)))) * EXP(\eta_1)$			
$\theta_1$ : CL typical value	5.61 (2.44)	(5.34;5.88)	
$\theta_5$ : Asymptotic (maximal) effect of Screat on CL	0.869 (1.28)	(0.847;0.891)	
$\theta_6$ : growth rate of CL	0.0334 (12.8)	(0.025;0.0418)	
$\theta_7$ : inflexion point of adults CL	110 (3.37)	(103;117)	
$\eta_1$ (IIV CL)	0.0450 (13.3)	(0.0333;0.0567)	CV=21.2%
$Q(L/h) = \theta_2(Weight/70)^{0.75} * EXP(\eta_2)$			
$\theta_2$ : Q typical value	4.15 (8.31)	(3.47;4.83)	
$\eta_2$ (IIV Q)	0.285 (28.0)	(0.128;0.442)	CV=53.2%
$\eta_{2,1}$ (cov CL, Q)	0.043 (39.5)	0.00968; 0.0763	R=38%
$V_1(L) = \theta_3(Weight/70) * EXP(\eta_3)$			
$\theta_3$ : $V_1$ typical value	7.55 (2.94)	(7.11;7.99)	
$\eta_3$ (IIV $V_1$ )	0.0724 (18.2)	(0.0465;0.0983)	CV=26.9%
$\eta_{3,1}$ (cov CL, $V_1$ )	-0.00177 (350)	-0.0139; 0.0104	R=3.1%
$\eta_{3,2}$ (cov Q, $V_1$ )	-0.116 (28.3)	-0.180; -0.0517	R=-80.8%
$V_2(L) = \theta_4(Weight/70) * EXP(\eta_4)$			
$\theta_4$ : $V_2$ typical value	4.80 (4.96)	(4.33;5.27)	
$\eta_4$ (IIV $V_2$ )	0.203 (17.6)	(0.133;0.273)	CV=45.1%
Residual error			
$\epsilon_1$ : proportional component	0.0206 (5.87)	(0.0182 ;0.0230)	CV=14.4%
OFV: 9422.311 - Run number EMA8 Condition Number: 92.2			

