This model will be considered as starting point for the modeling including pediatric patients (<2 years old) during structural model refinement. Depending on the preliminary checks, it will be either updated and refined after including pediatric patients <2 years to the existing dataset or considered as initial setting for building a pediatric population <2 years model. The inclusion of Japanese healthy volunteer data from GDX-44-013 study in this model will be performed later when the study on Japanese pediatric patients data will be completed and their data available for updating the model.

Once the structural model will be defined, the residual error model will be refined and finally the IIV will be introduced on the PK parameters for which the estimation of the variability can be supported by the data. At this step the error models will be diagonal (no covariance between variance components will be included).

	PH21036 / GDX-44-015 Analysis Plan Version 2.0: 29/10/2024	gadopiclenol Page 18/30
---	---	----------------------------

The selection of the most parsimonious structural model with appropriate IIV and residual error will be called the BASE model.

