## 12.1 SIMULATION IN CASE OF TERMINATION OF THE STUDY BEFORE COMPLETION OF THE RECRUITMENT

In the event that recruitment cannot be completed as planned at the end of the study, the exposure and PK parameters in non-recruited age groups will be determined by simulation.

The modeling steps (preliminary checks, model upgrade / refinement and validation) with the data available at end of study will be performed as specified in Section 9 and 10.

The refinement of the model will focus specifically on the impact of SCreat on elimination parameter since it is known that renal function is not mature before 1 year old and the current relationship does not account for the maturation in youngest patients.

In order to simulate a realistic pediatric (<2 years) population of patients in terms of association between gender, age, weight and SCreat levels, the 45 patients from the study DGD-44-063 will be used.

For each age group not recruited and to be simulated, two hundred individuals (100 female and 100 male) will be sampled, with replication, from the DGD-44-063 dataset.

The PK exposure parameters ( $C_{10}$ ,  $C_{20}$ ,  $C_{30}$  and  $AUC_{0-\infty}$ ) for the dose 0.05 mmol/kg will be simulated for these patients from the popPK model obtained after inclusion of the recruited patients.

The same simulations will be performed for all other paediatric age groups and for adults with normal renal function by resampling, for each age group, subjects from the available data (including GDX-44-015 for age group recruited, GDX-44-007 for pediatric subjects above 2 years old, GDX-44-003 and GDX-44-005 for adults with normal renal function).

The distribution of simulated parameters will be summarized graphically using box plots by age group. Moreover, 5th, 25th, 50th (median), 75th and 95th percentiles will be tabulated by age group.

The PK exposure parameters simulated from the refined model will be compared to those simulated from a model where the maturation of renal function is based on post-menstrual age (PMA) instead of SCreat.

The maturation function described by Rhodin *et al.* was used to describe the maturation of the renal fraction of elimination ( $MF_{renal}$ ), as shown in the following equation:

$$MF_{renal} = \frac{PMA^s}{PMA_{50}^s + PMA^s}$$

Where:

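### SAP 9.1–9.2 decides between pooled and infant-only data before adding the renal maturation that the tested model is known to lack; a refine-and-retest step is missing

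*SAP*

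**What the plan says.** SAP 6 sets out, among other aims, to assess whether the earlier model predicts exposure under 2 years and to update that model with the new data. SAP 9 takes the earlier model as its start, "with the objective to enrich and update the existing model if possible".

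SAP 9.1 step 1 makes the dataset depend on the preliminary checks: if the existing model predicts the infant data, they are added to the earlier data; "otherwise, only pediatric population <2 years data will be used for model development". Structural selection (step 2) and covariate work (steps 3 and 4) run on the dataset already chosen.

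SAP 9.2 gives two checks:
- The first is a prediction-corrected visual predictive check (pcVPC) from the existing model: "The measured concentrations should be fairly distributed within the simulated distribution".
- The second fixes the model parameters at their earlier estimates: "The variability terms (IIV and residuals) will be estimated".

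SAP 9.3 describes an earlier form in which "The CL was also scaled to eGFR with a power model for pediatric population", then the replacement requested by EMA. Table 2 gives "Gadopiclenol population PK model parameters estimates from the model refined for EMA submission and using Serum creatinine as covariate", and the text continues: "This model will be considered as starting point for the modeling including pediatric patients (<2 years old) during structural model refinement". Refinement follows the checks in both branches.

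SAP 12.1, written for early termination, says that "the current relationship does not account for the maturation in youngest patients" and supplies a maturation function of post-menstrual age (PMA). Protocol 11.2 and SAP 8.1 say that the sample-size simulations used a model already refined for renal maturation.

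**The concern.** The plan lets a model with a known gap decide whether all the older-patient data stay in the analysis. The correction is already written into the SAP, but it is not used at this decision. If the check fails only because maturation is missing, the result says nothing about whether infants and older patients can share a model once maturation is included.

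Two things are at stake. The objective of updating the adult and child model could go unmet. And between-patient variability in central volume (IIV V1) would be estimated from infants alone, with an expected median RSE of 95% at 45 subjects (Protocol Table 3). A smaller matter is that SAP 12 compares five age groups using the final dataset, and an infant-only dataset lacks four of them.

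**Working it through.** **1. The plan's own figures.** 45 / (1 − 0.10) = 50 patients, as stated. The Table 2 interval for typical CL is 5.61 ± 1.96 × (0.0244 × 5.61) = 5.34 to 5.88, as printed. The RSEs in Protocol Table 3 cannot be re-derived, because the simulation covariates are not given.

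**2. Creatinine factor on CL (SAP Table 2).** G(S) = 1 − 0.869·exp(−exp(−0.0334·(S − 110))). The unit is not stated; µmol/L is assumed. G = 1.000 at S = 40, 0.996 at 60, 0.943 at 80 and 0.876 at 90. The term barely lowers CL at low creatinine.

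**3. Maturation factor (SAP 12.1).** MF = PMA^3.4 / (47.7^3.4 + PMA^3.4) = 1 / (1 + (47.7/PMA)^3.4). With G near 1, Table 2 over-predicts typical CL by 1/MF if this function is true.

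| Age (term) | PMA, weeks | MF | Over-prediction of CL |
|---|---|---|---|
| Birth | 40 | 0.355 | 2.8 |
| 28 days | 44 | 0.432 | 2.3 |
| 3 months | 53 | 0.589 | 1.7 |
| 6 months | 66 | 0.751 | 1.33 |
| 12 months | 92 | 0.903 | 1.11 |

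**4. First check of SAP 9.2, simulated.** Inputs from the SAP: the Table 2 two-compartment model with its full variance matrix, residual variance 0.0206, 0.05 mmol/kg, and one sample per window. Assumed: 45 infants split 28/12/5 or 20/12/13 over Groups 1/2/3; ages uniform within group; weights from 3.4 kg at birth to 12.0 kg at 24 months; creatinine factor 1. There were 400 trials with 400 replicates each (Monte Carlo error up to 2.5 points). Entries are the percentage of trials with the observed median outside its 90% band (10% by chance).

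| True CL | Model tested | 10–60 min | 2–4 h | 6–8 h |
|---|---|---|---|---|
| Full MF | Table 2 | 98–100 | 100 | 100 |
| Half the deficit, 1 − 0.5(1 − MF) | Table 2 | 70–89 | 96–99 | 76–93 |
| No maturation | Table 2 | about 10 | about 10 | about 10 |
| Full MF | Table 2 with MF | about 10 | about 10 | about 10 |

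**5. Second check of SAP 9.2.** With typical CL fixed, the deficit must go into the random effects. For the two age mixes the mean of (ln MF)² is 0.24 and 0.39, so the apparent SD of the CL effect is √(0.045 + 0.24) = 0.53 to √(0.045 + 0.39) = 0.66. Simulated fits gave an IIV of CL of 52–64% CV, against 21% in Table 2, with a trend of the CL effect with age in every trial. This check would show the same misfit rather than rescue the model.

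**6. Chance exits.** SAP 10 reads three percentile lines; over three windows that makes nine bands. Even the correct maturation model leaves at least one of the nine in 57–65% of trials, and at least one of the three median bands in 26–29%.

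**7. What IIV V1 does to the 10-minute concentration (C10).** Under Table 2's matrix, removing the V1 effect cuts the variance of ln C10 by about 70%, and the ratio of the 97.5th to the 2.5th percentile falls from about 1.85 to 1.4. Under Protocol Table 3 values the share is 92–98%, and the ratio falls from 1.7 to 1.1.

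**The case against.** **Failure is not automatic.** A reader might infer that the check must fail. SAP 9.2 gives no threshold, and SAP 10 states its misspecification reading for the final model. The over-prediction also rests on the 12.1 function being true. Protocol 1.1 and 1.3 report that other gadolinium agents had similar pharmacokinetics in children and adults, although 1.3 also notes immature renal clearance. They do not say which parameter was similar, so no alternative factor can be derived from them. This objection stands as a limit on certainty.

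**Maturation is not ignored.** SAP 9.1 step 2 allows structural covariates, 9.3 foresees refinement and 9.5 lists age on clearance, in either branch. A reader might infer biased infant CL or AUC. The documents do not support that: the late timing affects which data are used, not whether maturation can be modelled.

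**A stand-alone infant model was foreseen.** Protocol 11.2 and SAP 8.1 accept poor precision of IIV V1 as of limited interest, and updating is planned only if possible. That is true. However, C10 is a primary criterion whose distribution is reported (Protocol 7.1 and 11.3.6), and it depends heavily on IIV V1. The same cannot be said firmly of the 20- and 30-minute concentrations: under Table 2's matrix most of the V1 contribution there disappears.

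**The precision cost of not pooling cannot be read from two tables.** A reader might set the 95% RSE beside the 18.2% in SAP Table 2. They are not comparable: the latter comes from earlier studies with no infants.

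**The tested model is sufficiently identified.** SAP 9.2 points to 9.3, which ends on Table 2; 9.5 keeps creatinine on clearance, and the workflow table in 12.1 calls the creatinine model current. Only the citation of reference 5 needs reconciling.

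**Conclusion.** The point holds as a matter of sequence: the pooling decision is taken on an unrefined model that the SAP itself calls incomplete for the youngest, and no retest is provided. If the SAP's PMA function holds, the check would very likely fail (median outside its band in about 99–100% of simulated trials, against about 10% with maturation). If only half of the deficit is real, failure is still likely. If there is no maturation effect, exits occur at chance level.

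The consequence is limited to possible loss of the older-patient data, with the update objective unmet and the spread of C10 resting on a poorly estimated IIV V1. The result depends on the assumed creatinine unit, weights and age mix, and on the maturation function. The change is a cheap improvement, not the repair of an analysis shown to be wrong.

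**What to change.** In SAP 9.1–9.2:

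1. Keep the existing-model check first, as the first analysis objective requires. If it fails, repeat it with a maturation term on CL, for example the function in 12.1, keeping the creatinine term. Use infant-only data only if the retest also fails.
2. Estimate PMA50 at the retest. If it is held at 47.7 when the truth is 45 or 50, the median leaves its 2–4 h band in 29–46% of trials. With 45 infants its expected RSE is 2–3% (other parameters fixed) or 4–5% (typical CL, Q, V1 and V2 also estimated).
3. State the retest criterion in advance, for example median lines and NPDE by age group, with an allowance for chance exits over three windows. Show individual points for the small Group 3.
4. Reconcile the reference 5 citation in SAP 9 and 9.1 with the Table 2 model in 9.3, 9.5 and 12.1.
5. Compute PMA from recorded gestational age where available, not from 40 weeks for all. Inclusion criterion 1 already turns on term status and, for preterm infants, the expected delivery date.
6. Add one sentence to SAP 12: in the infant-only branch, simulate the older groups from the earlier model and resampled earlier-study data, as 12.1 already describes.

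The cost is SAP wording, one extra model run and possibly one data field, with no added patient procedure. The downside is that a second chance to pool could hide misfit in the youngest, which is why item 3 asks for diagnostics by age group.

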## 9.2 PRELIMINARY CHECKS

In order to check if the existing model is predictive of data collected in pediatric population <2 years, some preliminary checks will be performed.

First, gadopiclenol concentrations in pediatric patients <2 years will be simulated using the existing model (see model definition in Section 9.3) and actual patients' settings (dose, sampling, characteristics). A prediction-corrected performance visual checks (pcVPC) approach will be used, simulating 1000 replicates of pediatric patients <2 years and plotting the distribution of these simulated concentrations with the actual measured concentrations. The pcVPC approaches are defined in Section 10. The measured concentrations should be fairly distributed within the simulated distribution.

In a second step, the existing model will be applied to pediatric population <2 years data with model's parameters fixed to the final estimates obtained in previous data. The variability terms (IIV and residuals) will be estimated. Diagnostic plots (as defined in Section 9.8) will be used to assess model misspecification.

Should any interim evaluation need to be performed during the course of the study to determine if exposure in any group of pediatric patients <2 years is as expected, the first step based on pcVPC will also be used for this purpose.

[figure not shown]
